5 PROCEDURES

5.1) Study procedures. Using lay language, provide a complete description of the study procedures, including the sequence, intervention or manipulation (if any), drug dosing information (if any), blood volumes and frequency of draws (if any), use of records, time required, and setting/location. If it is available: Upload a study flow sheet or table to **Zipline**.

For studies comparing standards of care: It is important to accurately identify the research procedures. See UW IRB POLICY
Risks of Harm from Standard Care and the draft guidance from the federal Office of Human Research Protections, "Guidance on Disclosing Reasonably Foreseeable Risks in Research Evaluating Standards of Care"; October 20, 2014.

Information about pediatric blood volume and frequency of draws that would qualify for expedited review can be found in this reference table on the Seattle Children's IRB website.

Nurses will be recruited to participate in a formative evaluation of an eLearning training in suicide prevention that includes participating in virtual training activities, completing surveys, completing training outcome assessments of skills using standardized patient role-plays, and participating in end-of-evaluation focus groups.

All study activities are detailed in Attachment: Nurse Study Activities & Remuneration.

There are 3-4 hours of training activities and 3 hours of research activities.

Training activities include 1 hour of didactics that includes reading material and watching video material, including skills demonstrating of suicide safety planning. Then, nurses practice skills of asking a virtual suicidal patient open-ended questions and making reflective statements using a chat bot (i.e., Client Bot Emily). The chat bot also provides feedback on skills practice. The third type of training activity is to practice suicide safety planning with a patient actor and receive feedback on general counseling skills used during the role-play through a computer program and feedback platform (i.e., Lyssn).

The training and technologies are further depicted/described in the Attachment: eLearning Approach.

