Research activities include completing surveys about knowledge, skills, motivation, and confidence in engaging patients around suicidality in general and safety planning in particular. Surveys will also include acceptability of and interest in using the technology for training. Standardized patient role-plays are also used to evaluate skills learned through the training process. End-of-evaluation focus groups of about 5 nurses each will provide insight into implementation barriers and facilitators of completing the training and of potentially doing safety planning with patients.

5.2 Recordings	s. Does the research involve creating audio or video recordings?
No	→ If no, go to question 5.3.
X Yes	\rightarrow If yes, verify that you have described what will be recorded in 5.1 and answer question a .
	a. Before recording, will consent for being recorded be obtained from subjects and any other
	individuals who may be recorded?
	No → If no, email [contact] before submitting this application in Zipline. In the email, include a brief description of the research and a note that individuals will be recorded without their advance consent.
	X Yes
(5.3)MRI scans.	Will any subjects have a Magnetic Resonance Imaging (MRI) scan as part of the study procedures?
	cans that are performed solely for research purposes or clinical scans that are modified for research purposes (for ng a gadolinium-based contrast agent when it is not required for clinical reasons).
X No	→ If no, go to question 5.4 .
Yes	→ If yes, answer questions a through c .
	a. Describe the MRI scan(s). Specifically:
	• What is the purpose of the scan(s)? Examples: obtain research data; safety assessment
	associated with a research procedure.

Describe the minimum and maximum number of scans per subject, and over what time period the scans will occur. For example: all subjects will undergo two MRI scans, six months apart.

Which subjects will receive an MRI scan?

	UWMC Radiology/Imaging Services (the UWMC clinical facility)
	DISC Diagnostic Imaging Sciences Center (UWMC research facility)
	CHN Center for Human Neuroscience MRI Center (Arts & Sciences research facility)
	BMIC Biomolecular Imaging Center (South Lake Union research facility)
	Harborview Radiology/Imaging Services (the Harborview clinical facility)
	SCCA Imaging Services
	Northwest Diagnostic Imaging
	Other: identify in the text box below:
_	

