Nurse training outcomes of general counseling skill quality and quality of safety planning will be assessed using standardized patient assessments. Nurses will complete four 30-minute role-plays over the course of the evaluation. These will be conducted by research staff/patient actors via Zoom, recorded, and assessed for general counseling skill quality using the Lyssn system. Pre- and post-training and follow-up role-plays will be assessed for fidelity to the safety planning intervention by the PI. Self-reported perception of skills will be assessed via survey at baseline, post-training and 6-months post-training using methods modified from training clinicians in evidence-based psychotherapy. Nurses will also complete **knowledge quizzes** of what is safety planning and how to do it.

Implementation barriers and facilitators will be assessed for both engaging in the training and using the skills learned with patients via nurse surveys at baseline, post-training and 6-months post-training as well as end-of-study focus groups. Questions will be designed using the TDF (e.g., beliefs about consequences, role & identity, environmental context & resources).

5.5 Data sources. For all types of data that will be accessed or collected for this research: Identify whether the data are being obtained from the subjects (or subjects' specimens) or whether they are being obtained from some other source (and identify the source).

If you have already provided this information in Question 5.1, you do not need to repeat the information here.

1. REDCap surveys

Research Electronic Data Capture (REDCap) is a HIPAA-compliant data capture system used by the UW and supported by UW's Institute of Translational Health Sciences. It will capture self-report survey data for this study, which are completed at baseline, post-training, and 6 months post-training.

2. Standardized patient role-play recordings & quality assessment

Nurses will be asked to complete four standardized patient role-plays with research staff or paid actors. These role-plays will be recorded. The Lyssn system will score the role-plays for general counseling skills. The PI will score the role-plays for quality of suicide safety planning. The results of scoring of role-plays will be kept on UW Medicine servers and in de-identified format.

3. Focus group recordings & transcripts

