 - For materials that cannot be uploaded: upload screenshots or written descriptions that are sufficient to enable the IRB to understand the types of data that will be collected and the nature of the experience for the participant. You may also provide URLs (website addresses) or written descriptions below. Examples of materials that usually cannot be uploaded: mobile apps; computer-administered test; licensed and restricted standardized tests.
 - For data that will be gathered in an evolving way: This refers to data collection/questions that are not pre-determined but rather are shaped during interactions with participants in response to observations and responses made during those interactions. If this applies to the proposed research, provide a description of the process by which the data collection/questions will be established during the interactions with subjects, how the data collection/questions will be documented, the topics likely to be addressed, the most sensitive type of information likely to be gathered, and the limitations (if any) on topics that will be raised or pursued.

Use this text box (if desired) to provide:

- Short written descriptions of materials that cannot be uploaded, such as URLs
- A description of the process that will be used for data that will be gathered in an evolving way.
- The general content of questionnaires, surveys and similar instruments for which general approval is being sought. (See the **NOTE** bullet point in the instructions above.)

1. Standardized patient role-plays

Nurses will be invited to participate in 4 total 30-minute standardized patients role-plays. These roleplays are designed to provide opportunities to practice skills in suicide safety planning using general counseling skills and as assessments of skills for evaluation purposes. Scenarios will be of patients hospitalized for medical/surgical/trauma reasons of varying adult ages. Nurses will receive feedback from the Lyssn system on one of the role-plays as part of the training. The PI will also assess the quality using a measure of suicide safety planning as part of the formative evaluation on pre and post-training role-plays. The computer coded and human coded data will be maintained in study records ongoing in a de-identified format and used for evaluation and refinement of the training program.

2. REDCap surveys

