Attachment: Nurse Study Activities & Remuneration

	Research Activities	Training & Research Activities			Research Activities						
Activities	1	2	3	4	5	6	7	8	9	10	11
	30 min	60 min	30 min	30 min	30 min	15 min	30 min	15 min	30 min	15 min	60 min
	Study orientation	Web-based	Standardized	Interact with	Standardized	Review Lyssn	Post-training	Post-training	6-month follow-	6-month follow-	End-of-study
	& baseline survey	didactic &	patient role-play	Client Bot Emily	patient role-play	feedback report	standardized	survey	up standardized	up survey	focus group
		demonstration					patient role-play		patient role-play		
Data collection	Demographics, pre-	Embedded	Post-web training	Tech use data	Post-Client Bot	Tech use data	Post-Lyssn	TDF constructs,	6-months post-	TDF constructs,	Implementation
	training TDF	knowledge	knowledge &		knowledge &		knowledge &	tech use,	training	skills use,	barriers &
	constructs	questions	skills		skills		skills	acceptability	knowledge &	acceptability	facilitators
									skills		
Remuneration	\$50	\$100	\$50	Included with #2	\$50	Included with #2	\$50	\$25	\$50	\$25	\$50
Week	1	1-2	2-3	3	3	-4	5	5		30	·

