Nurses will be recruited on an ongoing basis, which is expected to take about two months. Nurses will engage in 3-4 hours of training that is expected to take about one month to complete. Enrolled nurses will also engage in evaluation activities that will take 3 hours total. In the first month, this includes several standardized patient role-plays of suicide safety planning and survey measures. Six months after the training is completed, nurses will be asked to complete a 6-month standardized patient role-play, 6-month follow-up survey, and participate in an end-of-study 1-hour focus group. Some role-plays will serve dual purposes as part of the training as well as to collect training outcome data.

Primary Outcomes

Acceptability. Nurse training and technology acceptability will be assessed using the System Usability Scale (SUS), open-ended questions, and a modified version of the Client Satisfaction Questionnaire-8 (CSQ-8) to assess nurse satisfaction with the training.

Training outcomes. Nurse training outcomes of general counseling skill quality and quality of safety planning will be assessed using standardized patient assessments. Nurses will complete four 30-minute role-plays over the course of the evaluation. These will be conducted by research staff or paid actors via Zoom, recorded, and assessed for general counseling skill quality using the Lyssn system. Pre- and post-training and follow-up role-plays will be assessed for fidelity to the safety planning intervention by the PI. Self-reported perception of skills will be assessed via survey at baseline, post-training and 6-months post-training using methods modified from training clinicians in evidence-based psychotherapy.

Secondary Outcomes

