Quantitative data will be viewed graphically and analyzed descriptively. Qualitative open-ended responses to questions will be summarized into common themes or content analyzed, as appropriate. Acceptability of the training will be supported by scores above 24 (indicates average of 3) on the CSQ-8 provider-version, above 67 on the SUS, and responses to open-ended questions based on relevant TDF constructs. Feasibility of the training will be supported by nurse use statistics collected by the computer technology and completion of all training parts (web-based didactic, Client Bot, and Lyssn feedback). Focus group qualitative data will be content analyzed according to TDF constructs.

3. Human Subjects Considerations

Inclusion/exclusion Criteria

All nurses working on participating units will be eligible for participation. There are no exclusion criteria. Nurses will opt into the study based on interest and willingness, including willingness to utilize a computer and the internet to participate in the web-based training activities.

Informed Consent

Informed consent may occur in person, by phone, or by videoconference. The PI/research staff will send the informed consent document to nurses ahead of time and then meet to go over and explain the study, review the consent form, and answer any questions. We will obtain a waiver of documentation of informed consent to facilitate virtual consent procedures. Nurses are expected to be literate in English at the high school level. They are also expected to be able to use computer, internet, REDCap technology as they routinely use these or similar systems in their routine work.

Risks Associated with Study Participation

Confidentiality. Nurses may be concerned that performance on the standard patient role-plays and responses to study surveys and focus group questions may be shared with colleagues or supervisors. **Observation/assessment burden.** Completing training and research tasks may be perceived as burdensome and nurses may experience some performance-related anxiety on the standardized patients. Nurses may experience some frustration interacting with the technology, which may depend on nurse computer technology literacy.

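### Pre-training role-plays are promised, but all four scheduled role-plays follow the web didactic, so two role-play-based primary outcomes have no pre-training value

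*Combined protocol and SAP*

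**What the plan says.** **The promise.** Section 5.4 and the DSMP (section 2, Primary Outcomes) use the same sentence: "Pre- and post-training and follow-up role-plays will be assessed for fidelity to the safety planning intervention by the PI". Section 5.14, item 1, has the PI rate safety planning quality "as part of the formative evaluation on pre and post-training role-plays". Section 5.1 adds: "Standardized patient role-plays are also used to evaluate skills learned through the training process". Section 1.6 describes the study as longitudinal, with measurement before and after training.

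**What counts as training.** Section 5.1 puts the didactic first: "Training activities include 1 hour of didactics that includes reading material and watching video material". The DSMP Plan of Analysis defines feasibility partly by "completion of all training parts (web-based didactic, Client Bot, and Lyssn feedback"), so the didactic is one of three training parts.

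**The schedule.** The Nurse Study Activities & Remuneration attachment labels the data from the first role-play (activity 3) as "Post-web training" knowledge and skills. The only cell that uses the pre-training label belongs to activity 1, orientation and the baseline survey. It begins "Demographics, pre" and continues with training TDF constructs.

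**The third training outcome.** The same DSMP paragraph says: "Self-reported perception of skills will be assessed via survey at baseline, post-training and 6-months post-training".

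**The SAP.** It plans descriptive statistics for all outcomes, with means, standard deviations and confidence intervals across timepoints. It names no baseline and defines no change score.

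**The concern.** A design described as before-and-after training, with primary outcomes scored from pre-training role-plays, needs at least one role-play before training starts. The schedule has none. A score from activity 3, if reported as pre-training, already contains whatever the didactic achieved.

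This matters most for fidelity. According to the description of the eLearning approach, the didactic is where safety planning is explained and demonstrated, while the two technologies build general counseling skills. So the part that most directly teaches what the PI scores comes before the first measurement of it.

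The same outcome paragraph also mixes two starting points. Self-reported skill starts from a survey taken before any training, and role-play skill starts after the didactic. A reader who sees both called pre-post change would take them to cover the same interval. The results are meant to inform a larger trial, so the interval should be stated correctly.

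**Working it through.** **1. Is the schedule complete?** Tables can break in extraction, so the first check is whether a role-play has dropped out.

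- Count: role-plays are activities 3, 5, 7 and 9, so 4. This reproduces the four stated in sections 5.4, 5.5 and 5.14 and in the DSMP.
- Payment: 50 + 100 + 50 + 50 + 50 + 25 + 50 + 25 + 50 = $450, the total stated in section 4.4. Activities 4 and 6 are paid within activity 2.
- Research time: activities 1 and 7 to 11 give 30 + 30 + 15 + 30 + 15 + 60 = 180 minutes = 3 hours, as stated in section 5.1.
- Training time: activities 2 to 6 give 60 + 30 + 30 + 30 + 15 = 165 minutes = 2.75 hours, against a stated 3 to 4 hours. A missing fifth role-play cannot explain this gap, because the count would no longer be four and, at the table's $50 per role-play, the total would no longer be $450.

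No role-play is missing from the table.

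**2. Where do the role-plays fall relative to the didactic (activity 2)?**

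| Activity | Schedule's label for the data | Before the didactic? |
|---|---|---|
| 3 | after the web training | no |
| 5 | after Client Bot | no |
| 7 | after Lyssn | no |
| 9 | 6 months after training | no |

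Role-plays before the didactic: 0 of 4. Only activity 1 (orientation and baseline survey) comes earlier. Section 8.2b agrees: consent is followed by orientation, a demographic survey and the baseline survey, with no role-play.

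**3. Which training outcomes in the DSMP's Primary Outcomes have a pre-training value?**

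| Outcome | Source | First value | Pre-training? |
|---|---|---|---|
| General counseling skill | Lyssn score of role-plays | activity 3 | no |
| Safety planning fidelity | PI score of role-plays | activity 3 at the earliest | no |
| Self-reported skill | survey | activity 1 | yes |

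So 2 of 3 lack one. Acceptability, the other primary outcome, needs no baseline.

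**4. Which role-plays does the PI code?** There are four descriptions:

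- Section 5.4 and DSMP Primary Outcomes: pre-training, post-training and follow-up.
- Section 5.5, item 2: the role-plays, without limit.
- Section 5.14, item 1: pre- and post-training.
- DSMP section 4, Sources of Material: some of them.

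No single list reconciles these.

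**The case against.** **Pre-training may mean pre-technology.** This is the strongest reply. Section 1.5 and the DSMP say the new training accompanies a standard web didactic, and the eLearning description places the technologies after it. The schedule titles activity 7 as the post-training role-play and activity 9 as the 6-month follow-up. Those match two of the three labels in section 5.4, which leaves activity 3 as the natural candidate for the third. The reading is plausible and cannot be excluded. However, no text states it. Section 5.1 and the Plan of Analysis count the didactic as training, and the schedule reserves the pre-training label for the activity 1 survey. Even if this was the intention, the label still needs correcting.

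**The consequence is small.** This stands in large part. Acceptability is judged by CSQ-8 and SUS thresholds and open-ended responses, and feasibility by use data and completion. None of these uses role-play scores. There is no hypothesis test and no comparator, and enrolment is at most 20. The schedule's own label for activity 3 also lowers the risk of misreporting.

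**A stronger reading of section 5.14.** A reader might infer that it restricts PI coding to two role-plays and so leaves 6-month fidelity uncoded. The documents do not support that. Section 5.14 contains no restricting word, and the schedule itself describes the 6-month data as post-training. What stands is that the four descriptions differ and should be replaced by one list.

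**Conclusion.** The concern holds. The plan states a pre-training value for role-play outcomes and the schedule does not provide one: 0 of 4 role-plays precede the didactic, and 2 of the 3 training outcomes listed as primary have no pre-training value. Role-play change can be described only from after the didactic onward. The documents give no figure for the didactic's effect, so the amount missing from that change is unknown.

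A reader might go further and infer that the study could reach a wrong conclusion about the training. That does not follow: no success criterion depends on role-play scores, and no test or sample size is affected. The consequence is a mislabelled baseline and interval for a primary outcome. It should be fixed because the repair is cheap and changes what role-play change may be said to show.

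The conclusion rests on the didactic being part of the training, as section 5.1 and the Plan of Analysis say, and on the attachment being the operative schedule. That activity 3 is the role-play meant by pre-training is an inference, which the sponsor should confirm.

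**What to change.** Reconcile sections 1.6, 5.4 and 5.14 and the DSMP's Primary Outcomes with the activity schedule.

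**If the schedule stands:**

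1. Call activity 3 the post-didactic, pre-technology role-play wherever the text says pre-training role-play, after the sponsor confirms that this is the one meant. In section 1.6, limit the pre-post description to the survey measures.
2. Add to the SAP: *Role-play scores are described at activities 3, 5, 7 and 9 (Lyssn scores at all four; fidelity at those the PI codes), with activity 3 as the first value. Change from activity 3 excludes any effect of the web didactic and is not whole-training pre-post change. Self-reported skill change starts from the pre-training survey.* Keeping activity 5 preserves the step after each technology.
3. State once, by activity number, which role-plays the PI codes for fidelity. Make sections 5.4, 5.5 and 5.14 and DSMP sections 2 and 4 refer to that list.

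These are wording changes, with no effect on schedule, nurse burden, payment or sample. PI coding time depends only on which list the sponsor confirms.

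**If the text states the intention,** the schedule must change instead. Moving the first role-play ahead of activity 2 adds no time or payment but gives up the post-didactic measurement. Adding a role-play at the table's own 30 minutes and $50 gives 4 + 1 = 5 role-plays, 3 + 0.5 = 3.5 research hours and 450 + 50 = $500, and the stated totals would need updating.

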Observation/assessment burden. To manage potential performance anxiety related to the standardized patient role-plays, nurses will be reminded that the assessments will be used only for the research study and will not be shared with their supervisor or others who may use the information in an evaluative way. We will remind nurse participants that the purpose of our project is to develop effective training methods, not to evaluate them as professional nurse providers. Nurses will be reminded that all activities are voluntary, including the training activities. They will be allowed to quit using any of the training technology, end the session with the standardized patient, skip survey questions, and leave the focus group early or not answer questions if they choose. Nurses will have an opportunity to debrief with the research staff after the standardized patient. Nurses will be able to schedule the standardized patient to occur at their convenience.

Distress related to talking about suicide. Nurses will be allowed to end specific training or research activities if feeling distressed. The PI will be available to debrief nurses' experiences with training and research activities and nurses may reach the PI at her cell phone during the workday or the PI will return calls the following day. The PI will routinely reach out to nurses enrolled in the study and check in about their experience. The PI is a licensed clinical psychologist who routinely supervises and consults with mental health providers on managing distress associated with patient care. [name] has expertise in suicide prevention trials and training clinicians in suicide prevention and treatment and will also be available to consult with the PI on these issues.

Coercion. Nurses will be recruited by the PI/research team. The PI/research team will post advertisements, attend staff meetings, ask the unit nurse manager to send out a recruitment email, or email potential nurse participants directly to invite them to participate in the study. Nurses will be reminded that they can opt out of any part of the training and research activities and that whether they complete the activities is documented for research purposes and not reported to fellow nurses or supervisors. Remuneration was designed to balance adequate compensation for time and effort without being too large of an amount to be coercive.

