Data quality assurance includes monitoring data collection to ensure they are accurately and reliably collected and monitoring the storage of data to ensure they are stored securely and appropriately. Effective data quality assurance procedures involve proper training of staff in data collection procedures, use of appropriate data collection tools, and periodic review of adherence to data collection, transfer, and storage procedures as well as data completeness and accuracy.

The PI will develop manuals and procedures for data collection and storage, receiving guidance from mentors and consultants as appropriate, and will train research staff in these procedures.

Sources of Material

This study includes four primary sources of data collected for research purposes:

- a) Standardized patient role-play recordings Nurses will be asked to complete four standardized patient role-plays with research staff or paid actors. These role-plays will be recorded. Quality assessment scores will be generated by Lyssn as well as the PI coding of some of the role-plays as outcome assessments for suicide safety planning adherence.
- b) REDCap surveys

Research Electronic Data Capture (REDCap) is a HIPAA-compliant data capture system used by the UW and supported by UW's Institute of Translational Health Sciences. It will capture self-report survey data for this study, which are completed at baseline, post-training, and 6 months post-training.

c) Focus group recordings & transcripts

Nurses will be invited to participate in a 1-hour focus group with other study nurses to gather qualitative data about their experiences in the training and perceptions of implementation barriers and facilitators of other nurses utilizing the training and skills taught in safety planning.

d) Technology use data

The technologic innovations under study, including Client Bot and the Lyssn system will gather use data. Nurses will be provided access to the technologies in a fashion that allows use to be tracked internally by the systems.

Data Confidentiality

a) Standardized patient role-play recordings

Neither the recordings of standardized patient role-plays nor the individual quality assessment scores based on the role-plays will be shared outside of the research team. Scores will be maintained in de-identified format once downloaded from Lyssn or after PI coding of safety planning.

a) REDCap surveys

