- a) Standardized patient role-play recordings Standardized patient role-play scenarios will be developed by the research team for the purposes of the study. The PI will train research staff/standardized patient actors, in the scenarios. The PI will review standardized patient role-plays and provide feedback and retraining to staff/actors as needed. Research staff will test audio/video recording equipment prior to use. Audio/video recordings will be checked immediately following the role-play session for recording quality and any problems addressed prior to the next session. The PI has been trained in coding of suicide safety planning for quality and will ensure accurate downloading of Lyssn data and entry of quality assessment data.
- b) REDCap surveys All REDCap data collection surveys will be pilot tested by the research team. The surveys will be designed to reduce potential for human error in data entry or unintentionally skipping items. The PI and/or research staff will periodically review the survey data to ensure the tools are functioning properly.
- c) Focus group recordings & transcripts
 Research staff will test audio/video recording equipment prior to use. Audio/video recordings
 will be checked immediately following the focus group for recording quality and any problems
 addressed prior to the next session. The PI will review transcripts to ensure their quality.
- d) Technology use data

 The PI will work with technology consultants to ensure the technologies are accurately capturing usability data. The PI will ensure the data is transferred properly to the research team and is prepared appropriately for analysis. The PI and/or research staff will periodically review the technology use data captured to ensure the tools are functioning properly.

5. Event Reporting

The study team will follow procedures for reporting reportable events required of both the UW IRB (Guide to Reporting New Information - UW Research (washington.edu)) as well as NIMH (NIMH Reportable Events Policy).

The following Office of Human Research Protection (OHRP) Definitions will be used to meet reporting requirements:

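### Safety-planning fidelity, part of a primary outcome, is scored by the PI with no masking to timepoint or random scoring order described, so rater expectancy could not be told apart from a training gain

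*Combined protocol and SAP*

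**What the plan says.** **Who scores, and what.** Protocol section 5.5 (item 2) states: "The PI will score the role-plays for quality of suicide safety planning". DSMP section 2, under Primary Outcomes, gives the timepoints: "Pre- and post-training and follow-up role-plays will be assessed for fidelity to the safety planning intervention by the PI". Section 5.4 says the same. No other fidelity rater is named. General counselling skill on the same recordings is scored by the Lyssn software.

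**What the rater knows.** Section 5.6 says nurses can be identified on the Zoom recordings. Section 10.1 adds: "The PI will routinely reach out to nurses enrolled in the study and check in about their experience". The PI also watches role-plays for another purpose (DSMP section 4, Data Integrity): "The PI will review standardized patient role-plays and provide feedback and retraining to staff/actors as needed".

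**Safeguards stated.** DSMP section 4 says: "The PI has been trained in coding of suicide safety planning for quality". It also says: "The PI will develop manuals and procedures for data collection and storage". On de-identification it says: "Scores will be maintained in de-identified format once downloaded from Lyssn or after PI coding of safety planning". Section 12.3 gives co-investigators a role in checking data quality. Section 10.7 on un-blinding is answered as not applicable, but that item concerns group assignment.

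**Design and analysis.** Section 1.6 describes a pre-post longitudinal evaluation, with no comparison group. The SAP reports means, standard deviations and confidence intervals by timepoint. No test or threshold is set for fidelity.

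**The concern.** A fidelity rating is a human judgement. A rater who knows that a recording is post-training, and who built the training, may score it more generously without intending to. A control group rated by the same person would show some of that shift; here there is none. The shift has the same sign and form as a training effect, and recruiting more nurses does not reduce it. The other skill measures do not settle the matter: Lyssn measures a different construct, and perceived skill is the nurses' own report.

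A second route is drift in the rater's standard while working through the recordings. It matters only if scoring order follows timepoint, and the documents give neither the order nor the timing of scoring.

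What is at stake is how a change in fidelity can be read, and whether an unmasked rating procedure carries over into the larger trial that this study is meant to inform.

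**Working it through.** **1. Is the rater masked anywhere?** Each stated safeguard was compared with what masking would need.

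| Stated provision | Hides timepoint from rater? |
|---|---|
| PI trained in coding (DSMP 4) | No |
| PI writes data-collection manuals (DSMP 4) | Not described as doing so |
| Scores de-identified (DSMP 4) | No; this follows the PI's coding |
| Co-investigators check data quality (12.3) | No |
| Un-blinding item not applicable (10.7) | Concerns group assignment |

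No section describes hiding the timepoint or randomising the order.

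**2. Size of an expectancy shift.** The plan gives no figure to reproduce: no SD, effect size or rater-error estimate. The shifts below are therefore assumptions. Inputs: n = 20 (the maximum, sections 2.1 and 2.8) and n = 10 (assumed, for heavy loss).

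- Half-width of a 95% CI in SD units = t(0.975, n−1)/√n. At n = 20 this is 0.468; at n = 10 it is 0.715.
- Probability that the CI for one timepoint mean misses the true mean, by noncentral t with noncentrality = shift × √n:

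| Assumed shift | n = 20 | n = 10 |
|---|---|---|
| 0 | 0.050 | 0.050 |
| 0.1 SD | 0.071 | 0.059 |
| 0.25 SD | 0.186 | 0.109 |

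This is coverage of one mean, which is what the SAP will report. For a closer view of a false gain, take a 95% CI on each nurse's change, which the SAP does not specify. With no true gain, the probability that this CI lies wholly above zero is:

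| Assumed shift (SD of the change) | n = 20 | n = 10 |
|---|---|---|
| 0.2 | 0.133 | 0.082 |
| 0.3 | 0.246 | 0.134 |
| 0.5 | 0.564 | 0.293 |

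**3. Drift, by scoring order.** Assume that 20 nurses complete three scored role-plays each (60 recordings) and that the rater drifts linearly by 0.5 SD from first to last recording. The drift share is the difference in mean scoring position divided by 59.

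For collection order, DSMP section 2 says: "Nurses will be recruited on an ongoing basis, which is expected to take about two months". Take enrolment as uniform over 8.7 weeks, with role-plays at weeks 2.5, 5 and 30 (activities schedule; 2.5 is the midpoint of weeks 2–3).

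- P(one nurse's first role-play precedes another's post-training one) = 1 − 6.2²/(2 × 8.7²) = 0.746.
- Mean positions, counting from 0: first = 9.5 + 19 × 0.254 = 14.3; post-training = 9.5 + 1 + 19 × 0.746 = 24.7; 6-month = 40 + 9.5 = 49.5.
- Shares: about 10.4/59 = 0.176 and 35.2/59 = 0.596. Simulation gives 0.175 and 0.596.
- With recruitment over 6 to 12 weeks, the first share runs from 0.23 down to 0.14 and the second from 0.62 down to 0.58.

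| Scoring order | Share, first to post | Share, first to 6-month | Drift in SD (share × 0.5) |
|---|---|---|---|
| Collection order | 0.176 | 0.596 | 0.09 / 0.30 |
| Batched by timepoint | 20/59 = 0.339 | 40/59 = 0.678 | 0.17 / 0.34 |
| Nurse by nurse | 1/59 = 0.017 | 2/59 = 0.034 | 0.01 / 0.02 |
| Random | 0 on average (SD 0.094) | 0 on average (SD 0.094) | 0 on average |

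**The case against.** The strongest case is about weight. The stated aim is acceptability and engagement, effectiveness is left to later studies, and the analysis is descriptive. The numeric criteria in the DSMP Plan of Analysis apply to CSQ-8 and SUS scores, not fidelity. Even perfect masking would leave practice over four role-plays, and a first role-play that follows the web didactic, as other explanations or limits. The fidelity instrument is not described in detail; expectancy could be small for a present/absent checklist. The document is a lay-language ethics form with manuals still to be written, so silence is weaker evidence than it would be in a scoring manual. Finally, masking the same PI to nurses the PI knows can only be partial, and a scenario tied to a timepoint would give the occasion away.

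Most of this stands, and it limits the importance of the point. It does not remove it. The score is listed as primary, the plan lets a known bias enter it, and one rival explanation can be weakened at little cost. The assumed shifts and the drift table show what could happen, not what will. If masking is already planned, one sentence in the protocol settles the matter.

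**Conclusion.** The concern holds. As written, an expectancy shift by the single unmasked rater would be indistinguishable from a training gain in safety-planning fidelity. Its size is unknown. A 0.25 SD shift, if it occurred, would be about half the CI half-width at n = 20 and would raise non-coverage of a timepoint mean from 5% to 19% (11% at n = 10). A 0.1 SD shift would do little (7% and 6%). Drift adds anything between almost nothing and 0.34 SD under the assumed 0.5 SD total, depending on an order the plan does not state.

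The point is limited to descriptive fidelity results. It does not touch the Lyssn scores or the acceptability criteria. It is a worthwhile, inexpensive improvement and not a flaw that undermines the study. Confidence is medium, because the instrument and the scoring procedure are not described.

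**What to change.** Add to section 5.5 and the DSMP:

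- After the last 6-month role-play, existing research staff give each recording a random code, remove date and timepoint labels, and trim the actor's opening orientation (described in section 8.2).
- The PI then scores the recordings in random order.
- The PI's ongoing review of actor quality continues but assigns no fidelity scores.
- The report states that masking was partial and that rater agreement was not measured.

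**Cost.** File handling for 60 recordings (20 × 3), or 80 if all four role-plays are scored, by staff already on the study such as the research coordinator (section 12.3). The PI's load is unchanged at 60 × 0.5 h = 30 hours to 80 × 0.5 h = 40 hours of footage, and no rater is added.

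**Downsides.** Fidelity scores arrive only at the end. Nurses remain recognisable, the PI will have seen some recordings during actor review, and dialogue or scenario may reveal the occasion. Single-rater reliability stays unmeasured, and practice effects are untouched.

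**Separate reporting point, not evidence of bias.** Reconcile which role-plays are scored: section 5.14 says pre and post only, sections 5.4 and DSMP 2 add follow-up, section 5.5 sets no limit, and DSMP 4 refers to some of them. Describe the first role-play as post-didactic, in line with the activities schedule.
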